Vascular leak is a fundamental feature of CAs, mediating hemorrhage and the associated accumulation of non-heme iron (including hemosiderin). Pre-clinical studies demonstrated rescue of vascular permeability and decreased lesional iron deposition with ROCK inhibitors and statins³¹, and B-cell depletion therapy³² in murine CA models recapitulating the human disease. [name]'s group in Chicago implemented a novel MRI application of assessing iron deposition in human CAs using quantitative susceptibility mapping (QSM)³³⁻³⁶. Mean lesional QSM was shown to reflect actual iron concentrations assessed by mass spectroscopy in resected human CA specimens³⁵. Researchers in Chicago and New Mexico optimized a second technique, dynamic contrast enhanced quantitative perfusion (DCEQP) measure on MRI in human subjects, reflecting mechanistically postulated vascular hyper-permeability^{33, 34, 37-39}. The [name] team used both QSM and DCEQP successfully in over 200 CA subjects and showed strong inter-observer agreement in QSM and DCEQP measurements, stability of both measurements in clinically stable lesions, and reproducibility across MRI instrument platforms at the Chicago site^{36, 38}. As predicted by the conservation of mass hypothesis, CA lesions with greater permeability (K_i) had higher lesional iron content (QSM)³⁶, and lesional iron content was greater in older patients and in CAs with prior SH³⁶. More recent studies demonstrated a significant increase of mean lesional QSM and DCEQP K_i in human CA lesions manifesting interval SH or growth during longitudinal follow-up, while these did not change in stable lesions³³. There were tight, sensitive and specific thresholds of QSM and DCEQP increases in association with clinical events³³. Therefore, it is postulated that the QSM and DCEQP may be used as *in vivo* measures of hemorrhagic activity and vascular leak, respectively, and may reflect sensitive, clinically meaningful therapeutic effect in human CAs. No other biomarkers have been as linked mechanistically to CA, nor associated as closely with clinical events.

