5.1 INCLUSION CRITERIA

- (1) 18 years of age and older.
- (2) diagnosed with a brain CA (single or multiple).
- (3) had a SH within the past year (with demonstrated new lesional bleeding or hemorrhagic growth >3mm on diagnostic studies AND attributable new symptoms).
- (4) ~~no prior treatment of the symptomatic lesion (after neurosurgical consultation)~~. Subject is able to provide informed consent.

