8 STUDY ASSESSMENTS AND PROCEDURES

All eligible subjects will be identified by the study team at each site. Based on clinic schedules and current patient databases, all CCM patients with a symptomatic hemorrhage within the last 12 months (of screening) are eligible for the trial. Sites will screen neurology, neurosurgery, and neurointerventional radiology clinic schedules, MRI schedules, and attend Neurovascular rounds to help identify potential subjects. Additionally, study sites will rely on referrals from the various services listed above, or self-referrals via web searches and through the Angioma Alliance, a patient support group. Once identified, the study coordinator at each site, along with the site PI, will screen the subject for basic eligibility. Screened subjects not scheduled to come in for a clinical visit within their eligibility window will be contacted by the study coordinator or PI to explain the study and determine if the subject is interested. When the subject comes in, either for a standard clinic visit or for a study visit, the study team will review the subject's medical history to ensure the subject meets the inclusion criteria. The trial will be explained and informed consent obtained. After consent is obtained a physical exam (height, weight, vital signs) will be completed, a baseline modified Rankin Score obtained, and EQ-5D, PROMIS 29, and NIH stroke scale assessments completed. The study team will also collect information about the subject's history, pertinent to the disease (history of seizure, resection of other lesions, etc.). All subjects at the FUBV sites (enrolled to the FUBV arm) will have a MRI scan including the additional sequences for research as specified in Specific Aim 2 (QSM/DCEQP). All women of childbearing age will undergo a urine or serum beta-HCG pregnancy test prior to MRI to confirm no pregnancy, per local institutional guidelines.

Subjects enrolled in the FUBV arm will return for 2 follow up visits: one at 12 months and the other at 24 months. Excluding the informed consent process, all baseline procedures will be repeated. Subjects will have completed their participation upon completion of the baseline visit procedures (SCA arm) or the year 2 visit (FUBV arm). All subjects enrolled in the SCA arm will have one study visit only.

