univariable and multivariable logistic regression and reported as odds ratios and 95% CIs. Depending on the number of recurrent SH over the 2-year period, we may analyze re-bleeds as a continuous outcome and the associations of baseline features or biomarkers assessed using linear regression. Performance of final model(s) will be assessed using r^2 in the case of linear regression, area under the curve (AUC) and Hosmer Lemeshow goodness of-fit test⁵⁵ in the case of logistic regression, or concordance index in the case of Cox proportional hazards regression. AUCs between various models (univariable) will be compared using the method proposed by DeLong et al⁵⁶. For biomarkers, we will create a binary variable (yes/no) depending on whether the % change in mean lesional QSM or K_i during 1-year epochs exceed previously defined respective thresholds (+ 5.8% QSM and +39.6% for K_i)³³ that were significantly associated with new clinical events at high sensitivity and specificity in previously stable lesions. We will then assess the association of this newly created variable (“biomarker event”) with SH rate treated as continuous (using two sample t-test or Wilcoxon rank sum test) and binary (using Chi-square or Fisher’s exact test) outcomes of interest. Finally, we shall compare the sensitivity/specificity of changes in mRS, QOL, and NIHSS scores, and lesional QSM and K_i in relation to SH during the same epochs, using McNemar’s test with SH (yes/no binary) as the reference standard. All tests will be 2-sided and p-values <0.05 considered statistically significant.

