Follow-up and Biomarker Validation (FUBV) Sites: University of Chicago, University of New Mexico, Mayo, University of California San Francisco, and Johns Hopkins were chosen because of additional established infrastructure for advanced imaging, including identified MRI physicists, neuroradiologists and site engineers who will work with the Biomarker Imaging Core (BIC) on implementing QSM and DCEQP protocols. A subset of approximately 120 CASH cases will be enrolled at FUBV sites to perform imaging biomarker validation studies (Specific Aim 2) and follow-up of CASH cases annually for up to two years (Specific Aim 3) to evaluate changes in outcomes. This subset of CASH cases will undergo a research MRI scan at baseline and at 1 and 2-year follow-up visits and undergo modified Rankin Scale (mRS) score and EQ-5D, PROMIS 29, and NIHSS assessments. A target recruitment of 120 CASH cases over 3-4 years at the sites conducting the FUBV arm is amply justified, with demonstrated 256 CA cases recently evaluated per year at those sites, expecting to identify 38 CASH cases each year (15% prevalence). Utah and Barrow may also serve as alternate FUBV arm sites if needed, with large demonstrated CA clinical activity. The University of California San Francisco and Johns Hopkins are now part of the FUBV arm.

Assuming a sample size of 120 CASH cases, and allowing 30% dropouts or missing biomarker or other data, we would have 84 evaluable patients (168 patient-years). We project 10%-20% re-bleed rate/year, supported by population studies and meta-analyses of CASH^{18, 19}, with the higher estimate particularly applying to brainstem cases. We would hence expect 17-34 SHs. Based on this, for continuous outcomes we will have 80% power at an alpha level of 0.05, to detect a difference between the means of patients with and without re-bleeding of at least 0.63-0.77 standard deviation. For categorical outcomes (i.e. presence or absence of a risk factor) we will be able to detect a difference of 32-40% between these two groups. This allows testing of questions regarding the rate of SH, and the prevalence of other outcomes in relation to SH during follow-up (Specific Aim 3).

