9.4 STATISTICAL ANALYSES

9.4.1 GENERAL APPROACH

Data collection. Key variables to be collected in this study will be decided on by all stakeholders in Year 1. At a minimum, these will include patient demographics, genotype, baseline MRI lesion features of the hemorrhagic CA (size, location), time from SH, prior bleeds/dates, and diagnosis date. Functional status will be measured using the modified Rankin Scale (mRS) score⁵⁷, Euro-QoL⁵³, PROMIS29⁵², and NIH Stroke Scale. PROMIS 29 short forms are an assessment of anxiety, depression, and fatigue, and have been validated for use in several common neurological disorders. Presence of obstructive sleep apnea. Recent findings suggest that sleep apnea results in decreased blood flow to the brain. This transient ischemia may be implicated in CA hemorrhage. Sleep apnea questions will be included in the dataset and response analyses as described under the topic Predictors of SH.

Data harmonization. Common data elements from each site will be reviewed, updated, and harmonized using an iterative, stepwise process based on DataSHaPER (DataSchema and Harmonization Platform for Epidemiologic Research) recommendations⁵⁸⁻⁶⁰. Questionnaires, codebooks, and protocols, etc. at the 3 established CA databases (Table 2) will be compiled and distributed for review. A series of Executive Committee teleconference calls will be held in Year 1 to decide on a set of 'target' data elements for potential clinical trials, as has been similarly done with the consensus process for developing clinical guidelines paper¹⁷. The EDHC and DCC will then develop standardized electronic data entry forms and codebooks for data collection. Each site shall be trained in abstracting and entering data for their cases online. Data will be collected prospectively in Years 2-5. Analysis datasets will be generated quarterly by the DCC for quality control analysis by EDHC.

Event Rate: Time to recurrent SH will be analyzed using Kaplan Meier method and Cox proportional hazards regression approach. Rates of recurrent SH/patient/year from initial SH qualifying event, and SH/patient/year from enrollment (potentially more relevant for trial modeling) will be estimated along with 95% CIs.

Biomarker changes over 2 years: Changes in mRS, EQ-5D, PROMIS 29, and NIHSS scores, mean lesional QSM and K_i during 1 and 2-year epochs will be compared using paired t-test or Wilcoxon signed rank test to assess changes within patients over time, including 95% CIs.

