Predictors of SH: Two sample t-test or Wilcoxon rank sum test will be used to compare such changes between patients with and without recurrent SH. Categorical variables such as proportions of patients with a drop in mRS score ≥ 1 point, between patients with and without recurrent SH will be compared using Chi-square or Fisher's exact test. Associations of baseline characteristics (sex, lesion locations, familial/sporadic) and recurrent SH as a binary outcome (yes/no) will be assessed using univariable and multivariable logistic regression and reported as odds ratios and 95% CIs. Depending on the number of recurrent SH over the 2-year period, we may analyze re-bleeds as a continuous outcome and the associations of baseline features or biomarkers assessed using linear regression. Performance of final model(s) will be assessed using r^2 in the case of linear regression, area under the curve (AUC) and Hosmer Lemeshow goodness of-fit test⁵⁵ in the case of logistic regression, or concordance index in the case of Cox proportional hazards regression. AUCs between various models (univariable) will be compared using the method proposed by DeLong et al⁵⁶. For biomarkers, we will create a binary variable (yes/no) depending on whether the % change in mean lesional QSM or K_i during 1-year epochs exceed previously defined respective thresholds (+ 5.8% QSM and +39.6% for K_i) that were significantly associated with new clinical events at high sensitivity and specificity in previously stable lesions³³. We will then assess the association of this newly created variable ("biomarker event") with SH rate treated as both continuous (using two sample t-test or Wilcoxon rank sum test) and binary (using Chi-square or Fisher's exact test) outcomes of interest. Finally, we shall compare the sensitivity/specificity of changes in mRS, QOL, and NIHSS scores, and lesional QSM and K_i in relation to SH during the same epochs, using McNemar's test with SH (yes/no binary) as the reference standard. All tests will be two-sided and p-values <0.05 considered statistically significant.

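### Fixed QSM and K_i cut-offs taken from stable lesions are applied to recently bled lesions, and no planned analysis separates evolution of the index bleed from new activity

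*Combined protocol and SAP*

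**What the plan says.** - **Cut-offs.** Section 9.1 creates a yes/no biomarker event for each one-year epoch, according to whether the percent changes "exceed previously defined respective thresholds (+ 5.8% QSM and +39.6% for K_i". It describes these cut-offs as ones "that were significantly associated with new clinical events at high sensitivity and specificity in previously stable lesions". Section 9.4.1 repeats the rule and the qualification ("at high sensitivity and specificity in previously stable lesions").
- **Population.** Section 5.1 requires that the patient "had a SH within the past year". Section 8 counts the window back from screening: "all CCM patients with a symptomatic hemorrhage within the last 12 months (of screening) are eligible for the trial".
- **Scans.** Section 9.2: "This subset of CASH cases will undergo a research MRI scan at baseline and at 1 and 2-year follow-up visits". Section 1.3 ties the research sequences to a routine care appointment and sets no minimum or fixed interval from the SH.
- **Marker behaviour.** Section 4.2 reports a "significant increase of mean lesional QSM and DCEQP K_i in human CA lesions manifesting interval SH or growth during longitudinal follow-up", with no change in stable lesions. The same section says that the course of the markers in patients with a recent SH is not known.
- **Use of time since SH.** Section 9.4.1 collects "time from SH, prior bleeds/dates". Sections 9.1, 9.4.1 and 9.4.2 do not use it as a covariate, stratum or subgroup in any analysis of change.
- **Year 1 versus year 2.** The synopsis makes the similarity of biomarker change in the two years a secondary endpoint. Section 9.4.1 says it will be assessed, for sample size and trial length, and gives no method.

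**The concern.** A cut-off on change has a false-positive rate that depends on how far the marker moves when nothing new happens. In the source setting, as section 4.2 reports it, stable lesions did not move. In this cohort the first scan follows a bleed by an interval that varies between patients. If the marker is still rising at that scan, lesions without a re-bleed can cross the cut-off. If it is falling, a true re-bleed can stay below it.

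The sensitivity and specificity of QSM and K_i against SH are then compared with those of mRS, NIHSS and quality-of-life change by McNemar's test. The later milestones in section 10.1.2 use the relative sensitivity of the instruments to choose outcomes to take to the FDA. A marker could look poor or good there partly because of when its baseline scan was taken.

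**Working it through.** **1. The plan's own figures (section 9.2) reproduce.** Evaluable patients: 120 x 0.70 = 84. Patient-years: 84 x 2 = 168. Expected SHs: 168 x 0.10 = 16.8 and 168 x 0.20 = 33.6, the stated 17-34. A two-sided two-sample t-test at 80% power gives 0.770 SD (17 v 67) and 0.630 SD (34 v 50), as stated. Two proportions with continuity correction, with 20-50% in those without re-bleeding, give 38-40 and 32-33 points against the stated 32-40%. None of these depends on the point made here. The cut-offs come from a cited study and cannot be re-derived from the documents.

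**2. Time since the index SH, by epoch.** Inputs: SH 0-12 months before screening (sections 5.1 and 8) and visits at 12 and 24 months, each ±1 month (section 1.3). Assumption: the baseline scan is done at screening; if it is later, every figure shifts up.

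| Epoch | Starts (months after index SH) | Ends |
|---|---|---|
| Baseline to Year 1 | 0-12 | 0 + 11 = 11 to 12 + 13 = 25 |
| Year 1 to Year 2 | 11-25 | 0 + 23 = 23 to 12 + 25 = 37 |

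The starting ranges barely overlap, so evolution after the index bleed falls mainly in the first epoch. The second is not wholly free of the problem: patients who re-bleed unresected stay in follow-up (sections 4.3 and 7.1), so a year-1 re-bleeder starts year 2 from a recent SH.

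**3. Effect of drift on the fixed cut-off (illustration; drift, SD and re-bleed increment are assumed).** With normal percent change in patients who do not re-bleed:

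false-event rate = 1 - Φ((cut-off - mean drift) / SD)

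QSM, SD 5 points:
- drift 0: (5.8 - 0)/5 = 1.16, rate 12.3%
- drift +5: (5.8 - 5)/5 = 0.16, rate 43.6%
- drift -5: (5.8 + 5)/5 = 2.16, rate 1.5%

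Among the 84 - 17 = 67 patients without re-bleeding at 10% per year, that is about 8, 29 and 1. Across assumed SDs:

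| Marker | SD | Drift (points) | False-event rate |
|---|---|---|---|
| QSM | 3 | -5 / 0 / +5 | 0 / 2.7 / 39.5% |
| QSM | 5 | -5 / 0 / +5 | 1.5 / 12.3 / 43.6% |
| QSM | 10 | -5 / 0 / +5 | 14.0 / 28.1 / 46.8% |
| K_i | 25 | -20 / 0 / +20 | 0.9 / 5.7 / 21.7% |

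If a re-bleed adds an assumed 12 points of QSM (SD 5), sensitivity = 1 - Φ((5.8 - drift - 12)/5), which is 59.5 / 89.3 / 98.7% at drift -5 / 0 / +5. Specificity is 98.5 / 87.7 / 56.4%.

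**4. Mean change, re-bleed versus no re-bleed.** If both groups share drift d, the difference is (d + effect) - d = effect, and d cancels. Bias needs time from SH, or drift itself, to differ between the groups. The plan does not check this.

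**5. What a year-2-only analysis would have.** First re-bleeds in year 2 among patients free of SH in year 1: 84 x 0.9 x 0.1 = 7.6 and 84 x 0.8 x 0.2 = 13.4, so about 8-13. With year 1 included (84 x 0.1 = 8.4 and 84 x 0.2 = 16.8), first re-bleeds total 16.0 and 30.2. An observed sensitivity of 6/8 has an exact 95% CI of 35-97%; 10/13 has 46-95%.

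**The case against.** **The enrollment-based epoch is the setting that matters.** Section 4.2 gives the likely trial population as patients with SH in the prior year, so future trials would also take baseline at a variable time after the bleed. Using the existing cut-offs from enrollment measures how they perform in that use. This stands as a reason to keep the baseline-to-Year-1 epoch. It does not remove the need to show how much of the result depends on time since SH.

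**A reader might infer that the year 1 versus year 2 comparison is confounded.** The documents do not support that. Time since the bleed is part of what separates the two years, and section 9.4.1 wants the difference in order to set trial length and sample size. The unadjusted contrast is the right one.

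**A reader might infer that re-bleeds will be missed because the marker falls back after the index bleed.** On the arithmetic, full return after a rise of exactly the cut-off would show as 1/1.058 - 1 = -5.5% (QSM) or 1/1.396 - 1 = -28.4% (K_i). The documents give no such course. For QSM, section 4.2 points the other way, with more lesional iron in lesions that had bled before.

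**A reader might say that no enrolled lesion is stable at baseline.** That goes too far: the term is not defined in these documents, and a scan 11-12 months after the SH could qualify.

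**The plan does not rest on the cut-offs alone.** Continuous change is compared between groups, and section 9.1 plans AUCs for logistic models, although it does not clearly plan an ROC for percent change. The explicit rules for rejecting QSM or DCEQP in section 10.1.2 depend on validation and quality assurance, not on this variable. Both points limit the damage.

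**Conclusion.** The mismatch is in the plan's own text. Cut-offs credited with good performance in stable lesions are scored in patients who bled within a year of screening, from a baseline at no fixed time after the bleed, with the intervening course declared unknown. Any drift after the index bleed enters the fixed-cut-off sensitivity and specificity, mainly in the first epoch, and the planned analyses cannot tell it from new activity.

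The size cannot be stated from the documents. The rates in the working show only that modest drift could matter, and with no drift there is no bias. The conclusion covers the fixed-cut-off results. For mean differences by re-bleed status it is conditional, as in step 4. It does not extend to the stated sample-size figures or to the planned year comparison. For mRS, NIHSS and quality of life the argument is by analogy; the documents give no recovery course. This is a worthwhile, inexpensive improvement, not a flaw that invalidates Aim 3.

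**What to change.** Change the SAP wording as follows; no new visits or variables are needed.

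- (a) Keep both epochs. Report biomarker-event sensitivity and specificity separately for baseline to Year 1 and Year 1 to Year 2, and by time from the most recent SH to the scan that starts the epoch. Patients who re-bled in year 1 are then identifiable in year 2.
- (b) In the comparisons of change in QSM, K_i, mRS, NIHSS and quality of life between patients with and without recurrent SH, include time from the qualifying SH to baseline as a covariate.
- (c) Report the ROC for continuous percent change in QSM and K_i in this cohort, with confidence intervals, beside the fixed cut-offs.
- (d) Keep the unadjusted year 1 versus year 2 comparison for trial design, and show it by time from SH as a supporting analysis.

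Do not make Year 1 to Year 2 the sole primary threshold analysis: it would rest on about 8-13 first re-bleeds and would set aside the epoch that starts at enrollment.

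Cost: one covariate is spent, item (b) needs a regression model in place of a two-sample test, and the strata are small, so the stratified estimates will be imprecise and should be read as descriptive.

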Moderate to severe disability after SH has been reported in 11-22% of patients^{17, 40-42}. A CA re-bleed causes significantly greater disability than initial SH²². The proportion of CASH cases with any functional disability varied between 26 and 65% at U Chicago, Mayo and BVMC cohorts. Only two studies assessed QOL in CAs, and both were limited to surgical patients. One study⁴³ used Karnofsky performance scale, Patzold Rating and SF-36, and the second⁴⁴ used only SF-36. Newer QoL scores (e.g. EQ-5D and PROMIS 29) have been validated and are more specific for stroke patients compared to SF-36⁴⁵⁻⁵³, and easier to obtain than the Patzold Rating⁵⁴. No study to date has reported QOL measures or their changes over time in CASH patients observed without surgery. **It would be useful to assess functional outcome and QOL measures at baseline and document their change over time with or without a symptomatic re-bleed.** One or more may be fit for use as a putative outcome in clinical trials of pharmacotherapies, and may even be useful in future surgical trials. As to the QSM and DCEQP biomarkers of lesional hemorrhage and permeability, even if they are successfully and reliably deployed at multiple sites, **it remains unclear how they change during longitudinal follow-up in cases with CASH, and whether their changes are more sensitive than clinical events.** The gaps of knowledge regarding outcome measures in clinical trials are addressed in Specific Aim 3 of this proposal.

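### Aim 3 scores the biomarkers only against symptomatic hemorrhage, so it cannot show that they are more sensitive than clinical events; the epoch-level tests also ignore that a patient can contribute two epochs

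*Combined protocol and SAP*

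**What the plan says.** **The question.** Section 4.2 lists as unknown how QSM and DCEQP change over follow-up in these patients and "whether their changes are more sensitive than clinical events". It then states: "The gaps of knowledge regarding outcome measures in clinical trials are addressed in Specific Aim 3 of this proposal".

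**The analysis.** Section 9.1 (Specific Aim 3) defines a yes/no biomarker event according to whether the percentage change in QSM or K_i "during 1-year epochs exceed previously defined respective thresholds", namely +5.8% for QSM and +39.6% for K_i. These cut-offs come from earlier work, as values "that were significantly associated with new clinical events at high sensitivity and specificity in previously stable lesions". The biomarker event is related to SH by chi-square or Fisher's exact test when SH is binary. Last, the plan will "compare the sensitivity/specificity of changes in mRS, QOL, and NIHSS scores, and lesional QSM and K_i in relation to SH" over the same epochs, by McNemar's test "with SH (yes/no binary) as the reference standard". Section 9.4.1 repeats this: "using McNemar's test with SH (yes/no binary) as the reference standard".

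**What counts as SH.** Section 5.1 requires new lesional bleeding or growth on imaging together with new attributable symptoms. Section 2.2 accepts that lesions in less critical brain regions might bleed just as often while going clinically unnoticed.

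**Timing and size.** The follow-up (FUBV) arm is scanned at baseline, Year 1 and Year 2 (Sections 1.2 and 1.3). Section 9.2 expects 84 evaluable patients, 168 patient-years and 17 to 34 SHs.

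**The concern.** The yardstick is also the thing the biomarkers are meant to be compared with. Scored against itself, SH has sensitivity and specificity of 100%, so no data could place a biomarker above it. A biomarker event in an epoch without SH is recorded as an error, although a subclinical bleed is exactly what a more sensitive marker should pick up. A biomarker that detects more hemorrhagic activity than SH would therefore lose apparent specificity and gain no apparent sensitivity. Readers who look to Aim 3 for the answer to the question in Section 4.2 would not find it there, and could take low specificity as evidence against a useful marker.

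The second issue is the unit of analysis. Biomarker events are defined on one-year epochs, so a patient with all three scans supplies two, and the Year 1 scan ends one and starts the other. The plan does not say whether epochs are pooled, and it names no method for within-patient dependence.

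**Working it through.** **1. The plan's own figures.** 120 × 0.70 = 84 evaluable patients. 84 × 2 = 168 patient-years. 168 × 0.10 = 16.8 and 168 × 0.20 = 33.6, which agree with the stated 17–34 SHs. The detectable differences in Section 9.2 also reproduce. A two-sided t-test at 0.05 with 80% power gives 0.770 SD (17 v 67 patients) and 0.630 SD (34 v 50), as stated. Continuity-corrected maximum differences in proportions are 0.400 and 0.329, against the stated 32–40%. None of these figures covers the McNemar comparison, for which no power is given.

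**2. What the reference standard permits.** With SH as reference:
- sensitivity of SH = specificity of SH = 100%, by identity;
- biomarker sensitivity = (biomarker+, SH+) / (all SH+), which is at most 100% and does not involve the SH-negative epochs;
- biomarker specificity = (biomarker−, SH−) / (all SH−), which falls with every biomarker event outside an SH epoch.

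Evidence that a biomarker finds more than SH can lie only in the biomarker+, SH− cell, and that cell enters only as error.

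**3. Illustration (assumed).** Take 168 epochs, with 84 patients each giving two complete epochs. Let 25 contain SH (within 17–34), leaving 143 without, and let a biomarker event occur in 80% of SH epochs: 0.80 × 25 = 20. The 80% and the rates in the first column are assumptions.

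| Event rate in non-SH epochs | Events without SH | All biomarker events | Ratio to 25 SH epochs | Specificity |
|---|---|---|---|---|
| 10% | 14.3 | 34 | 1.4 | 90% |
| 20% | 28.6 | 49 | 1.9 | 80% |
| 30% | 42.9 | 63 | 2.5 | 70% |

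Sensitivity is 80% in every row.

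**4. A better marker that does not look better (assumed).** Let true hemorrhagic activity occur at twice the SH rate, with SH a subset of it. SH then truly detects 50% of activity. Give the biomarker sensitivity s of 0.8–1.0 and specificity 0.95 for activity. With SH rate p, apparent specificity against SH is 1 − [p·s + (1 − 2p)(0.05)] / (1 − p).
- p = 0.10, s = 0.8: 1 − (0.08 + 0.04)/0.90 = 0.87; s = 1.0: 1 − (0.10 + 0.04)/0.90 = 0.84.
- p = 0.20, s = 0.8: 1 − (0.16 + 0.03)/0.80 = 0.76; s = 1.0: 1 − (0.20 + 0.03)/0.80 = 0.71.

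The marker truly detects 80–100% of activity against 50% for SH, yet under the planned scoring it never exceeds SH.

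**5. Counting events does not measure sensitivity either.** The 43 extra events in the last row of the table could all be subclinical bleeds or all be measurement noise; the table is identical. If there is no subclinical bleeding at all (p = 0.10, s = 1.0, specificity 0.95), the biomarker-event rate is 0.10 + 0.90 × 0.05 = 0.145, which is 1.45 times the SH rate from noise alone. With 168 epochs treated as independent, a paired test would call that a difference with about 79% power. In the doubled-activity settings of step 4 the power is 94% or more. The comparison is feasible at this sample size, but its result has to be called event yield.

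**6. Dependence between epochs.** For a proportion over two epochs per patient with within-patient correlation ρ, the variance is multiplied by 1 + ρ. Patients prone to bleeding push ρ above zero, and naive standard errors are then too small. The shared scan works the other way. If independent error of variance σ² affects each scan, the two changes have covariance −σ² and variance 2σ² each, so error alone gives ρ = −σ²/2σ² = −0.5 on the continuous scale. The documents give no ρ, so neither the direction nor the size of the net error can be fixed in advance.

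**The case against.** The strongest reply is that SH is the yardstick in this sentence and not a competitor. McNemar's test against a common reference is a standard way to compare several instruments, and a candidate surrogate for SH has to be scored against SH. That stands: the planned analysis is valid for ranking QSM, K_i, mRS, QOL and NIHSS as detectors of SH, although sensitivity would rest on only 17 to 34 events.

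It can also be said that the phrase about being more sensitive than clinical events appears in the rationale and not in the wording of Aim 3 or the endpoints, and that sensitive might mean responsive over time. The plan does give SH rates and within-patient biomarker changes with confidence intervals, and a biomarker-event by SH table would show the counts. Those are useful ingredients, but no head-to-head comparison is specified, and Section 4.2 does assign the gap to Aim 3. If McNemar's test were read as each biomarker event against SH, it would compare the two frequencies; the text, however, describes sensitivity and specificity.

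A reader might go further and infer that the choice between SH alone and other outcomes hangs on this test. Section 10.1.2 bases that decision on the interim or final analyses of the aims in general and does not name it. Nor does the plan commit to reporting predictive values.

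On clustering, the objection that pooling is not stated is fair. Parts of Section 9.1 compare patients, and the power calculation uses 84 patients. The concern is therefore conditional on epochs being the unit.

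**Conclusion.** The point holds as a mismatch between a question and its analysis, and it should be corrected. The planned comparison answers which instrument best detects SH. Whether a biomarker detects more than SH is left unanswered, and symptomless bleeding is classed as error. This rests on the definitions of sensitivity and specificity and on the plan's own definition of SH; it needs no assumed number. The event counts (34, 49 or 63 against 25) and the doubled-activity model only illustrate how large the hidden excess could be. They depend on assumed event rates, complete follow-up in 84 patients and independent epochs.

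The documents do not support saying that the planned analysis is invalid, or that a higher biomarker-event frequency would itself prove greater sensitivity. The Aim 3 sample-size figures are sound. If epochs are pooled, unclustered McNemar, chi-square and Fisher tests will have wrong standard errors, by an amount and in a direction that cannot be stated beforehand.

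**What to change.** 1. In Sections 9.1 and 9.4.1, label the planned sensitivity and specificity as agreement with SH, and limit their conclusion to detection of SH.
2. Add a prespecified paired comparison, on the same epochs, of the proportion with a biomarker event and the proportion with SH, as a difference or ratio with 95% CI. Report it as relative event yield and not as sensitivity, and state that an excess may reflect subclinical bleeding or measurement noise. Where the standard MRI sequences already collected allow, cross-tabulate the biomarker-positive, SH-negative epochs against new lesional bleeding or growth regardless of symptoms, read without knowledge of the QSM and K_i results.
3. State the unit of analysis. Where it is the epoch, use GEE or a bootstrap that resamples patients for all tests and confidence intervals.

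The cost is a few lines of SAP text, some extra analysis of data already collected (with a blinded read where the imaging cross-tabulation is done), and a more cautious interpretation of the biomarker results. No new visits or scans are needed.
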